12. SAFETY ASSESSMENT

Adverse Events Definitions

In this study, an Adverse Event (AE) is any undesirable clinical occurrence (sign, symptom, illness, or other medical event), that appears or worsens during the clinical study, or requires medical treatment or intervention to a subject, whether it is considered to be device related or not. If an adverse event occurs, the first concern will be the safety and welfare of the subject. Appropriate medical intervention will be made.

Any AE or complication reported by the subject or observed by the physician that occurs during or after treatment with the device will be recorded in the subject's medical record or source document and on the Adverse Event Case Report Form. The investigator will determine if the AEs are device related or procedure related. This assessment shall include the onset date, resolution date, severity, seriousness, frequency, treatment and outcome.

Each AE should be assessed according to the following criteria:

Severity

Each AE should be assessed for its severity, or the intensity of an event experienced by the subject.

Mild: Awareness of a sign or symptom that does not interfere with the subject's activity or is transient resolved without treatment and has no sequelae.

Moderate: May interfere with the subject's usual activity and require additional intervention and/or treatment, and may have additional sequelae.

Severe: Significant discomfort to the subject and/or interferes with the subject's activity. Additional intervention and or treatment are necessary. Additional sequelae occur. Severe is used to describe the intensity of an event experienced by the subject.

Adverse Device Effect (ADE)

Each AE should be assessed for its relationship to the device or procedure as identified as follows:

Device: This category should be restricted to adverse events directly attributable to the effect of the device.

Procedure: A procedure is any activity that supports the usage of the device.

Use the following categories for assigning the certainty of the relatedness:

Related: The AE is known to occur with the study agent, there is a reasonable possibility that the study agent caused the AE, or there is a temporal relationship between the study agent and event. Reasonable possibility means that there is evidence to suggest a causal relationship between the study agent and the AE.

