Not Related: There is not a reasonable possibility that the administration of the study agent caused the event, there is no temporal relationship between the study agent and event onset, or an alternate etiology has been established.

Pre-existing Conditions

A pre-existing condition should not be reported as an adverse event unless there has been a substantial increase in severity or frequency of problems, which has not been attributed to natural history.

Diagnosis of Adverse Event

There should be an attempt to report a “diagnosis” rather than the individual signs, symptoms and abnormal laboratory values associated with the diagnosis. However, a diagnosis should be reported only if, in the Investigator’s judgment, it is relatively certain (i.e., definite or possible). Otherwise individual signs, symptoms and abnormal laboratory values should be reported as the adverse events.

Anticipated Outcome Related Adverse Events

Anticipated adverse events in this study may include: temporary minor skin irritation, redness or swelling which may last from a few minutes to a few hours, minor swelling in the treated area for up to a week or slight heat discomfort during treatment. Very rarely, there may be possible bruising, burns, hyperpigmentation (skin turns darker) or hypopigmentation (skin turns lighter).

Any anticipated AE that occurs at any time during or after the use of the study device must be reported by the Investigator to Venus Concept. If the anticipated AE, in the opinion of Venus Concept or the Investigator, is likely to affect the safety of the subjects or the conduct of the study, the Research Ethics Board (REB)/Institutional Research Board (IRB) will be notified of the event within 10 working days after Venus Concept first receives notice of it.

Unanticipated Adverse Device Effects (UADE)

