14. STATISTICAL CONSIDERATIONS

Statistical Design

This study is a randomized, open-label, multi-centre study.

Sample Size

Enrollment will continue until up to 100 evaluable subjects have been recruited to the study. Any subject removed from the study in accordance with the provisions of this protocol will be replaced by other subject.

Statistical Methods

All subjects who received any amount of treatment will be included in the report. The primary outcome measure is the subject's overall tolerability of the adjuvant combination treatment as compared to the standard of care post fractional RF treatment. The self-assessment will be based on a 5-point Likert scale - Subject Tolerability Scale (Appendix A). Summary statistics will be generated for subject tolerability immediately after treatment, 24 hours and 72 hours following

treatment as per the terms: Very tolerable, tolerable, having no opinion, intolerable and very intolerable.

The secondary outcomes measures are the subject's degree of discomfort and/or pain as measured by the visual analogue scale (VAS), the incidence of spontaneous adverse events (AEs) and the investigator's assessment of improvement using the Fitzpatrick Wrinkle and Elastosis Scale scores before and after treatment as well as Global Aesthetic Improvement Scale (GAIS) for each subject. VAS scores from the treated group will be compared with the VAS scores of the standard of care group. The investigator's assessment of improvement using the Fitzpatrick Wrinkle and Elastosis Scale from the treatment group will be compared with that of the standard of care group. The GAIS scores for both groups will also be compared.

Summary statistics will also be generated for all treatment emergent adverse events (TEAs). The following types will be reported:

- Overall TEAEs
- Severe TEAEs
- TEAEs related to treatment
- Serious Adverse Events (SAEs)
- SAEs related to treatment
- TEAEs leading to treatment discontinuation

15. DATA HANDLING and RECORD KEEPING

Confidentiality

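### The Related and Not Related definitions overlap, because timing alone is enough for Related, so the written rule does not determine the planned summaries of related TEAEs and related SAEs

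*Combined protocol and SAP*

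**What the plan says.** Section 12 (Safety Assessment, Adverse Device Effect) gives the investigator two categories for relatedness and no third.

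- **Related** has three alternatives. The entry opens "Related: The AE is known to occur with the study agent", continues "there is a reasonable possibility that the study agent caused the AE", and closes "or there is a temporal relationship between the study agent and event". A further sentence explains the middle alternative: "Reasonable possibility means that there is evidence to suggest a causal relationship between the study agent and the AE". It explains only that phrase and puts no condition on the temporal alternative.
- **Not Related** also has three alternatives. The first is "There is not a reasonable possibility that the administration of the study agent caused the event". The other two are "there is no temporal relationship between the study agent and event onset, or an alternate etiology has been established".

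Section 12 gives no order of precedence, no time window for a temporal relationship and no adjudication step. Section 14 (Statistical Methods) lists "TEAEs related to treatment" and "SAEs related to treatment" as outputs separate from overall TEAEs and SAEs. It does not redefine related.

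**The concern.** With only two categories, every event should fall into exactly one. Here each category is an or-list, and the lists are not complements of each other. Timing alone is sufficient for Related, while lack of evidence for causation, or a proven other cause, is sufficient for Not Related. Many events can have both features.

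This matters because subjects are asked about adverse events shortly after treatment: by telephone at 24 and 72 hours after the first treatment and 24 hours after the second, and at the 72-hour follow-up visit (Sections 11.2 and 11.3). Close timing will be common among the events captured. The trial is open-label (Section 5), the investigator assigns relatedness (Section 12), and nothing hides the arm from whoever makes that choice. Adverse-event incidence is a secondary outcome of this tolerability study (Section 7), so the related-event summaries are part of its safety message.

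**Working it through.** No sample-size or power figure is involved. The check is whether the two definitions divide events cleanly.

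**Inputs, all from Section 12.** Four yes/no facts about an event:
- K: a recognised effect of the agent
- P: a reasonable possibility of causation
- T: a temporal relationship
- A: another cause established

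**Rules as written.**
- Related = K or P or T
- Not Related = (not P) or (not T) or A

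**Count over the 2 × 2 × 2 × 2 = 16 combinations.**
- Related fails only when K, P and T are all absent. A is then free, so it fails in 2 and is met in 16 − 2 = 14.
- Not Related fails only when P and T are present and A is absent. K is then free, so it fails in 2 and is met in 16 − 2 = 14.
- No combination fails both, because that would need P to be both absent and present.
- Combinations meeting both: 14 + 14 − 16 = 12.

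| Reading | Both | Related only | Not Related only | Neither |
|---|---|---|---|---|
| As written, all 16 | 12 | 2 | 2 | 0 |
| As written, T present (8) | 6 | 2 | 0 | 0 |
| As written, A and P never together (12) | 8 | 2 | 2 | 0 |
| Not Related list read with and (16) | 1 | 13 | 1 | 1 |

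Reading the second list with and goes against its wording. It still leaves one double classification and one gap, and timing alone still makes an event Related.

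**Does the overlap survive sensible restrictions?** Suppose that an established other cause rules out P (removes 4 combinations), that a recognised effect always implies P (removes 4 more), and that P requires T (removes the remaining 2 with P but not T). Then 16 − 4 − 4 − 2 = 6 combinations are left. All ten removed were in the both group, so 12 − 10 = 2 still meet both. Those two have T present and K and P absent, one with and one without a proven other cause. The overlap that survives therefore comes from the stand-alone timing criterion.

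**What this means for the tables.** If every doubly classified event is coded Related, the related count is the number of events with K or P or T. If every such event is coded Not Related, it is the number with P and T and not A. Any count between these complies with the protocol. The documents contain no event data from which to size the gap.

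**Check of the fix.** Related = P with Not Related = not P gives 8 and 8 of 16, with none in both and none in neither. If a recognised effect is to be sufficient by itself, Related = K or P gives 12, and its complement gives 4 (K and P absent, T and A free). That pair also has no overlap and no gap.

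**The case against.** The strongest reply is that the defect is smaller than it looks.

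- **A count will exist.** A reader might infer that the related tables have no number at all. The documents do not support that. The investigator decides relatedness, so each event will presumably be coded once. The weakness is that the definitions do not determine the code.
- **Temporal relationship is not defined as any onset after treatment.** A reader might infer that nearly every TEAE becomes Related and that the related table copies the overall one. That needs an assumption the documents do not make. Not Related expressly allows for events with no temporal relationship, and treatments are three weeks apart, so a later event need not be temporally linked.
- **The expected events may be clear-cut.** The local skin reactions anticipated in Section 12, with no other cause, would be recognised, plausible and well timed, so Related only. The conflict group could be small.
- **There is a partial causal filter.** Section 12 restricts the device label to events directly attributable to the device. The procedure label has no such limit, so this does not settle the matter.
- **Consequences are bounded.** Overall TEAEs, severe TEAEs, overall SAEs and discontinuations do not use the relatedness code. Section 12 requires every SAE to be reported whatever its relatedness. Nothing shows that the ambiguity favours one arm.

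All of this limits the size of the point, but none of it makes the two definitions exclusive. It also stands that the definitions speak of an agent, the assessment of device or procedure, and Section 14 of treatment. That mismatch is a separate matter, which complementary wording alone would not resolve.

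**Conclusion.** The point holds as a defect in a stated rule. Under the text, an event soon after treatment with a proven other cause, or with timing and no evidence of causation, is both Related and Not Related. The related-TEAE and related-SAE summaries therefore depend on which definition the investigator applies, and the arm is known when that is done.

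The size is logical, not numerical: 12 of 16 combinations overlap, or 6 of 8 with a temporal relationship present, and 2 of 6 under the most restrictive reading examined. A reader might take 12 of 16 as the share of events miscounted; it is not, because combinations are not equally frequent. A reader might also take the lowest possible related count to be all events less those with an established other cause. Not Related also covers events with no reasonable possibility and events with no temporal relationship, so the count can go lower.

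The conclusion rests on reading or in its ordinary sense in both lists and on there being no precedence rule elsewhere in the documents. Overall TEAE and SAE counts and the primary endpoint are unaffected. The change should be made, but the trial's main result does not turn on it.

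**What to change.** Before any event is coded, replace the two definitions in Section 12 with a complementary pair and stop treating timing as sufficient by itself. For example:

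- Related: there is a reasonable possibility that the treatment caused the event, meaning evidence that points to causation, including that the event is already recognised as an effect of the treatment. Timing and any other established cause are weighed in reaching this judgement.
- Not Related: every other event.

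Put the same wording in the CRF completion guidance. Other complementary pairs would also work; what is needed is that each event meets one definition only.

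The cost is two sentences in Section 12 and the matching CRF text. Related counts may be lower than under a literal timing-only reading, though this is not certain because the present rule does not fix the count. The judgement remains unblinded, and investigators may still differ on what is reasonably possible. The change removes only the disagreement that the definitions themselves create. Making it later would mean recoding events with the arm known.

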11.1 Screening Visit

The following procedures will be performed at the screening visit:

- Written informed consent
- Assign unique identifying number
- Inclusion/exclusion criteria
- Demographics
- Physical examination
- Medical history
- Concomitant medications
- Skin type (Fitzpatrick Scale)
- Wrinkle evaluation (Fitzpatrick Wrinkle and Elastosis Scale)
- Test spot

Test Spot

In order to assess tolerability to treatment, up to three test spots will be performed on the area adjacent to the ear on the side of the neck close to the back (so as it is not visible). Test spots should be based on skin type and desired outcome as per the chart below. The test spots will be used to determine the optimal parameters / setting combinations prior to the first treatment and later, the second treatment.

- Following the test spot, wait to ensure that the chosen parameters indeed lead to the appropriate immediate response.

- If slight erythema and edema and no adverse events occurred, treatment should be continued using the same setting or increase by not higher than ~10% parameters for each session.
- If no results are observed, the treatment parameters should be increased.
- If the patient has experienced adverse events along with improvement, the treatment parameters should be decreased.
- Fine-tuning of the parameters can be done before proceeding to treat the entire sub-area with the chosen parameters. Modification of parameters per treated area within a treatment session should only be carried out if required due to safety concerns.

Assessment of the test spot will be performed following at least 2 hours and up to 48 hours depending on skin type. As such, the first treatment may be conducted on the same day as screening. It is important to not start treatment prior to full evaluation of the reaction to the test spot and having optimal parameters identified.

Table 1 - Test spot and treatment parameter chart

Starting parameters			
Skin Type	Mild	Moderate	Intense
I-II	220v / 30ms	250v / 15ms	280v / 15ms
III-IV	220v / 15ms	240v / 15ms	240v / 30ms
V-VI	220v / 10ms	230v / 5ms	240v / 5ms

Test Spots Mild			
Skin Type	Mild spot 1	Mild spot 2	Mild spot 3
I-II	220v / 5ms	220v / 15ms	220v / 30ms
III-IV	220v / 5ms	220v / 10ms	220v / 15ms
V-VI	220v / 5ms	220v / 8ms	220v / 10ms

Test Spots Moderate			
Skin Type	Moderate spot 1	Moderate spot 2	Moderate spot 3
I-II	250v / 5ms	250v / 10ms	250v / 15ms
III-IV	240v / 5ms	240v / 10ms	240v / 15ms

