- The immediate responses, indicative of the desired effect, are erythema and edema in the immediate area of the stamp and possibly also around it. The edema usually appears 1-2 minutes post-treatment and reaches its peak (of up to moderate edema) within 30 minutes. It should be noted that erythema is not easily noticeable, if at all, in darker skin types, so the edema will indicate a more significant effect in these subjects.
- Treatment consists of a single pass over the designated area.
- Unless otherwise instructed, the energy parameters can be modified between the treatment visits, as per the Investigator's discretion.
- It is recommended that throughout the study, that one staff member administer the treatments and another staff member perform the evaluations of the treatment area.

Post Fractional RF Treatment

- Subject Discomfort Assessment recorded on a 100mm visual analogue scale (VAS) immediately post treatment.
- Subject Tolerability Scale immediately post treatment.
- Subjects will receive either the adjuvant combination treatment (SCR Complex™ followed by Bio Cel™ occlusive gel applied to the treatment area) or SOC (no topical applications to treatment for 24 hours post fractional RF treatment).
- Subjects will be asked to complete the Subject Home Tolerability Scale at 24 hours and 72 hours post-treatment
- Subjects will be provided with the Subject Home Instruction Sheet (Appendix B).
- A follow-up telephone call will be made to the subject 24 and 72 hours after the first treatment and 24 hours after the second treatment. Study staff will ask the subject to report on the treatment using the Self-Report Adverse Event Questionnaire (Appendix C) and remind the subject to complete and return to the clinic with their completed Subject Home Tolerability Scale at each visit.

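### Sections 11 and 12 disagree on whether expected erythema and edema are adverse events, so the overall TEAE rate depends on which section a site follows, and counting them dilutes any arm difference in other events

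*Combined protocol and SAP*

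**What the plan says.** **Section 11.2 (Treatment Visits)** describes the reaction as intended: "The immediate responses, indicative of the desired effect, are erythema and edema in the immediate area of the stamp". It adds that edema usually appears 1-2 minutes after treatment and peaks within 30 minutes. The topical combination is applied only after the RF treatment.

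**Section 11.1 (Screening Visit, test spot)** keeps the reaction apart from adverse events: "If slight erythema and edema and no adverse events occurred".

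**Section 12 (Safety Assessment)** points both ways. Its general definition is that "an Adverse Event (AE) is any undesirable clinical occurrence", which could be read to leave out a desired response. Its list of anticipated adverse events, however, includes "temporary minor skin irritation, redness or swelling which may last from a few minutes to a few hours", and it goes on: "Any anticipated AE that occurs at any time during or after the use of the study device must be reported by the Investigator". It makes no exception for the intended response.

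**Sections 7 and 14.** The incidence of spontaneous adverse events is a named secondary endpoint. Section 14 plans summary statistics for "Overall TEAEs" and for severe, treatment-related, serious, related serious and discontinuation events. None of these categories sets the expected RF reaction apart.

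**The concern.** Both sections describe the same physical signs: erythema is redness and edema is swelling. An investigator who follows Section 12 literally enters them on the adverse event form for most treated subjects. One who follows Section 11, or leans on the word undesirable in the definition, may enter them for few. The study has two centres and is open-label, so the same reaction can be recorded differently by site, and staff may know the arm when they decide. A reaction that was never entered cannot be recovered at analysis.

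Two features of data collection add to the uncertainty. The endpoint refers to spontaneous events, yet the Appendix C questionnaire asks every subject directly about changes in the treatment area. Appendix B tells subjects to expect tiny scabs at 24-72 hours, which is when the telephone calls after the first treatment fall, but Section 12 does not list scabs among the anticipated events. Their status is undefined as well.

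At stake is whether the overall TEAE table can be read as a comparison of the topical with standard of care, or mainly reflects how each site recorded a normal response to the device.

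**Working it through.** **No figure in the plan to reproduce.** Section 14 gives up to 100 evaluable subjects with no alpha, power, effect size, event rate or allocation ratio. No expected TEAE rate appears anywhere. All rates below are assumptions, chosen to show how dilution works.

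**Inputs**
- Total of 100 (Section 14). Two arms (Section 8). Equal allocation, 50 per arm, is assumed.
- r: the proportion of subjects with any other TEAE, assumed 5% in one arm and 25% in the other. The test treats the arms symmetrically, so either arm may be the higher.
- q: the proportion in whom the RF reaction is recorded as an AE, assumed equal in both arms and independent of other events. Equality is plausible because edema begins 1-2 minutes after RF and the topical follows RF. The topical could alter how severe the reaction is or how long it lasts, but hardly whether it occurs.

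**Formula.** Overall TEAE rate = 1 - (1 - q)(1 - r). The arm difference is therefore (1 - q) × (0.25 - 0.05) = (1 - q) × 0.20.

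For example, at q = 0.50 the rates are 1 - 0.50 × 0.95 = 52.5% and 1 - 0.50 × 0.75 = 62.5%, a difference of 10 points.

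**Results** (exact power, Fisher test, two-sided 5%, 50 per arm)

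| q | Overall TEAE rates | Difference | Power |
|---|---|---|---|
| 0 | 5.0% v 25.0% | 20 points | 75% |
| 0.25 | 28.75% v 43.75% | 15 points | 27% |
| 0.50 | 52.5% v 62.5% | 10 points | 13% |
| 0.95 | 95.25% v 96.25% | 1 point | 0.6% |

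The difference in other events is the same in every row. Only the recording of the RF reaction changes. Most of the power is gone at q = 0.25, where the overall rates are nowhere near 100%.

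**Sites that differ.** Suppose two equal sites, one recording at q = 0.95 and the other at q = 0. The pooled rates are (95.25 + 5)/2 = 50.1% and (96.25 + 25)/2 = 60.6%. Treating the pooled counts as binomial, power is about 14%.

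**Does a high rate alone remove the contrast?** No. At 50 per arm, 95% v 75% also has 75% power. What matters is adding to both arms a response that the topical cannot prevent.

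**The other tables.** The treatment-related TEAE table shares the problem, because Section 12 accepts a temporal relationship as enough to call an event related. The severe, serious and discontinuation tables need not be affected.

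**The case against.** The strongest reply is that the documents already contain the answer. An AE must be undesirable, Section 11.2 calls the reaction desired, and Section 12 says only that anticipated events may include redness and swelling. A sensible site would leave the expected response off the form. Moreover, no test of TEAEs is planned, so power is lost in an analysis that the plan does not contain. Severity and resolution date are already recorded for each AE, so a separate table could be made at reporting.

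Part of this stands. The undesirable wording does allow a site to leave the reaction out, and the TEAE analysis is descriptive. Power here serves only as a measure of how much arm contrast the table can carry. But the mandatory reporting sentence allows the opposite reading equally well, and nothing says which governs. A later split works only if the reactions were recorded consistently. Resolution dates also cannot measure signs that last minutes to hours.

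A reader might go further and infer that overall TEAE incidence will sit near 100% in both arms and so cannot show any topical effect. The documents do not support that: they give no TEAE rate, and one reading of them leads to few recorded events. A reader might also take AE incidence to be the only between-arm safety measure. It is not: Section 14 lists six TEAE and SAE categories, and tolerability and VAS are also compared between arms. Nor do the documents state an expected severity profile for the topical products, so the severe-event table cannot be dismissed on that ground.

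**Conclusion.** The conflict between Sections 11 and 12 is in the text, and nothing in Section 14 resolves it. Depending on the section followed, the overall TEAE rate may be high in both arms, low, or site-dependent. Where the RF reaction is counted, a difference in other events shrinks in proportion to 1 - q. Under the assumed 5% v 25%, power falls from 75% to 27%, 13% and 0.6% as q goes from 0 to 0.25, 0.50 and 0.95. Those figures rest on 50 per arm, equal q in both arms, and independence of the two kinds of event. They illustrate the mechanism and do not forecast this trial.

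The consequence is limited to a descriptively summarised secondary endpoint and its treatment-related subset. The primary Likert tolerability endpoint is unaffected. The point is worth correcting before enrolment because inconsistent recording cannot be repaired afterwards.

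**What to change.** 1. Reconcile Sections 11.1, 11.2 and 12 into one written rule, applied at both sites, on whether and when expected erythema and edema are recorded as adverse events. State the status of the Appendix B scabs in the same rule.
2. Record the expected local RF reactions for every subject on a local-reaction line of the CRF, with severity and with duration in hours or by clock time.
3. In Section 14, tabulate these reactions by arm, showing severity and duration, separately from all other TEAEs.
4. Keep the all-events table so that nothing drops out of the safety report.

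The cost is one CRF line with a time field and one extra table. The change concerns recording and reporting only and alters no treatment.
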